6.2.3 Elimination criteria

- Withdrawal of the consent letter under information.
- Presentation of a serious adverse event.
- Non-tolerability or hypersensitivity to any of the compounds used during the tests (fluorescein, lissamine green , tetracaine)
- Non-tolerability or hypersensitivity to any of the investigational drugs.
- Adherence < 50% determined by subject's diary.

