6.3.2.1 Procedure for monitoring adherence

For more than four decades, numerous studies have been conducted on the appropriate way to measure and quantify medication adherence, but none have reached a consensus that could serve as the gold standard, whether in cross-sectional or longitudinal studies. [34] [35] [36] [37] [38] [39] [40] [41]

There are different procedures for measuring adherence to pharmacological interventions. The most common procedure involves self-reports , which include patient interviews, questionnaires, and self-monitoring diaries. Their strengths are speed, flexibility, low cost, and ease of implementation; they have a high degree of specificity for non-adherence, but their sensitivity and reliability for adherence are low. [41] [42]

Biochemical measurement of the drug, or its metabolite, is one of the methods that best confirms drug use. However, in addition to being costly and impractical, it is of little use in ophthalmic applications, as peripheral concentrations may be undetectable; and samples from other tissues require more invasive methods that would be inadvisable. [41]

Medication counting is another way to measure adherence. Classically referred to as "pill counting," in ophthalmology it is translated as the weight of the bottle. This is a simple, inexpensive, and noninvasive method. The main disadvantages of this method are: 1. It cannot confirm medication application (it could have been intentionally dropped or instilled outside the eye), and 2. It depends on the subject bringing the medication back. [41] [42]

A multi-method approach to adherence measurement is recommended. Because there is no ideal adherence measure, it is appropriate to use more than one method when aiming to achieve results that resemble reality. Selecting two or more methods allows for balancing their strengths and weaknesses, thus more accurately capturing adherence levels. [40]

Adherence assessment will be facilitated by the subject's diary and will be performed as follows:

$$Ad = (A_r)100/A_i$$

Ad= Adhesion

A_r= Registered applications

A_i= Applications indicated for the intervention

Final adherence will be determined by the average adherence from each visit. Overall adherence (all subjects) will be determined by the average of each subject's final adherence.

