For adverse event reporting, all eyes of participants randomized to an intervention group after the baseline visit will be considered. Results will be expressed as the number of cases (eyes).

The final results report will be displayed in tables or graphs, as appropriate.

The investigational drug will be considered safe and tolerable when there are no clinical or statistical differences in all primary outcome variables compared to its comparators.

Subjects with an adherence rate greater than 60% will be included in the statistical analysis to meet the study objective, based on the subject's diary. However, even if the subject's diary indicates adherence greater than 60%, if the adherence calculated by weight is less than 30%, the subject will not be included. The minimum dose necessary to obtain a pharmacological effect (lubricant/1 gel application per day) and the presence of adverse events (exposure) were considered sufficient to meet the overall design objective, in accordance with the pharmacological characteristics of the investigational product.

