8.3.3 Population analysis and missing data handling

An intention-to-treat analysis will be performed, including data from participants who completed at least visit 1.

9. Methods. Monitoring

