Excelencia en oftálmicos

Statistical Analysis Plan

Phase I clinical study, to evaluate the safety and tolerability of PRO-165 ophthalmic gel versus Artelac® Nighttime Gel, on the ocular surface of ophthalmologically and clinically healthy subjects.

Date of creation: July 2017.

Phase I clinical study, to evaluate the safety and tolerability of PRO-165 ophthalmic gel versus Artelac® Nightime Gel, on the ocular surface of ophthalmologically and clinically healthy subjects.

Protocol Code: SOPH165-0217/I.

Protocol Version: 2.0

Content

1.0	Abbreviations.....	3
2.0	Objectives of the Study.....	3
3.0	Study Design SOPH165-0217/I.....	4
4.0	Sample Size.....	5
5.0	Sample Size Calculation.....	6
7.0	Methods of Analysis.....	11
8.0	Changes.....	15
9.0	References.....	13
10.0	Annexes.....	16

Abbreviations

BHc	Complete hematic biometry
CRF	Electronic Case Report Form
VA	Visual Ability
AE	Adverse events
HR	Heart rate
FCI	Informed Consent Form
FR	Respiratory rate
HC	Conjunctival hyperemia
ICO	Eye Comfort Index
ITT	Population by intent to treat
SC	Safety call
MC	Concomitant medication
PFH	Liver function tests
RP	Research Product
IOP	Intraocular pressure
PP	Population by protocol
PRO-165	Chondroitin sulfate 0.18%/Sodium hyaluronate 0.2%
BC	Blood chemistry
SBP	Systemic blood pressure
TBUT	Tear break-up time
BV	Initial visit
FV	Final visit

Objective of the Study

To evaluate the safety and tolerability of the PRO-165 formulation on the ocular surface of ophthalmologically and clinically healthy subjects.

Study Hypothesis

H0: PRO-165 Ophthalmic Gel has a similar safety and tolerability profile to Artelac® Nighttime Gel in ophthalmologically and clinically healthy subjects.

H1: PRO-165 Ophthalmic Gel has a different safety and tolerability profile than Artelac® Nighttime Gel in ophthalmologically and clinically healthy subjects.

Study Design SOPH165-0217/I

Phase I, controlled, parallel-group, double-blind, randomized, exploratory clinical trial.

Duration of treatment

Treatment: 10 days.

Study period: 4 months.

Table 1. Study timeline

Procedures	Scrutiny	Basal Visit	Visit 1	Final Visit	Call Security
	Day 0 - X ^{to}	Day 0	Day 5 ± 2	Day 11 to + 1	Day 13 ± 1
CI Signature	X				
Medical history	X				
Ophthalmological medical history	X				
Laboratory sample collection	X			X	
Review of Laboratory Tests		X			X
Pregnancy Test	X			X	
Eligibility Criteria	X	Xb			
Allocation		X			

Chondroitin Sulfate 0.18%/Sodium Hyaluronate 0.2%

Delivery of intervention	Xc			

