- Intra-group difference: McNemar test. This is applied to 2x2 contingency tables with a dichotomous feature, with pairs of paired subjects, to determine if the marginal frequencies of row and column are equal (marginal homogeneity).
- Difference between groups: Pearson's Chi-square (χ^2) test or Fisher's exact test at expected values less than 5.

The level of difference to consider significance (p) will be an alpha (α) of 0.05 or less.

Chondroitin Sulfate 0.18%/Sodium Hyaluronate 0.2%

For the reporting of adverse events, all eyes of those participants who were randomly assigned to an intervention group after PI instillation (ITT) will be considered.

The final report of the results will be shown in tables or graphs, as appropriate.

Those subjects who meet a minimum adherence of 60% will be included in the statistical analysis to meet the objective of the study, taken from the subject's diary. However, even if the subject's adherence is greater than 60% per diary, if the adherence calculated by weight is less than 30%, the subject will not be included.

The investigational drug will be considered safe and tolerable when there are no clinical and statistical differences in all primary outcome variables, with respect to its comparator (Artelac® Nighttime Gel).

Table 3. Triangulation of concepts

Variable Type	Variable	A1	B1	B2	C1	D1	E1	E2	E3	E4	E5	E6	E7	E8
Background														
A1	Demographic			DT										
Basal														
B1	Medical History		DT			T								
B2	Comprehensive ophthalmological evaluation		DT	DT		TB			TB		B	B		T
Safety														
C1	Incidence of AD			TB	TB		TB	TB	TB		TB	TB	TB	TB
Tolerability														
D1	ICO			DB			DB							
Secondary outcome														
E1	TRL			DB		TB		DB						
E2	Vitals			DB		TB			B					

Chondroitin Sulfate 0.18%/Sodium Hyaluronate 0.2%

E3	Posterior segment	DB	TB	B
E4	Quality Questionnaire			TB
E5	PIO	DB	TB	B
E6	Visual Ability	DB	TB	B
E7	Laboratory tests	DB	TB	B
E8	Ocular surface stains	TB	TB	TB

D. Descriptive Statistics; T, 2x2 contingency table; B, Bivariate Analysis; M, Multivariate Analysis.

Changes

1. First version of the document, no changes apply.

Author of the document

Ph.D. in Cs. [name].

Biostatistics.

Clinical Operations.

Laboratorios Sophia, S.A. de C.V.

[name]

[name]

References

<https://doi.org/10.1007/BF03163747>.

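### The comfort-index comparison is filtered on adherence, conflicts with the stated intention-to-treat set and has no missing-index rule, so subjects who stop for intolerance can drop out of it

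*Protocol*

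**What the plan says.** **Variable and timing.** Protocol 6.4.1.1 and the SAP list of outcome variables make the comfort index the primary tolerability variable. Protocol 6.4.4, 6.5 and 6.5.1.4 place it at baseline and at the final visit (day 11, +1), with nothing in between.

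**Adherence filter.** Protocol 8.3.1: "Subjects with an adherence rate greater than 60% will be included in the statistical analysis to meet the study objective". The SAP, Methods of Analysis: "Those subjects who meet a minimum adherence of 60% will be included in the statistical analysis". Both also remove anyone whose weight-based adherence is below 30%. Protocol 6.3.2.1 defines the diary figure: "Final adherence will be determined by the average adherence from each visit".

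**A different set.** Protocol 8.3.3, whose heading also covers missing data, consists of one sentence: "An intention-to-treat analysis will be performed, including data from participants who completed at least visit 1".

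**SAP labels.** ITT is used only for adverse events, for subjects "randomly assigned to an intervention group after PI instillation (ITT) will be considered". The abbreviations list includes PP ("Population by protocol"), which is never defined or attached to an analysis.

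**Elimination.** Protocol 6.2.3 lists "Non-tolerability or hypersensitivity to any of the investigational drugs" and diary adherence below 50%.

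**Success.** Protocol 8.3.1 calls the product safe and tolerable when there are "no clinical or statistical differences in all primary outcome variables". The SAP has nearly the same rule.

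**The concern.** Adherence is observed after randomisation, and a subject who finds the gel uncomfortable is likely to use it less or stop. Filtering a tolerability score on adherence therefore selects on something linked to the outcome. The elimination criterion for non-tolerability works the same way if eliminated subjects' data are not kept. A subject who does not return has no post-treatment index at all, and no rule says what then happens.

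The direction matters because success is the absence of a difference. If intolerance is commoner with PRO-165 and those subjects leave the index comparison, the remaining subjects look more alike and the tolerability claim becomes easier to meet. With 16 subjects per group, two or three people can matter. Choosing among conflicting set definitions after the data are in would also be hard to defend.

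**Working it through.** The plan gives no figure for this point, so there is none to reproduce. The check is a comparison of the rules, followed by an illustration of size.

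**1. Which rule reaches the index?** Both documents apply the filter to the analysis that serves the study objective. Protocol 5.5.1 gives that objective as safety and tolerability, so the filter covers the index. Only adverse events have an explicit set without it.

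**2. The rules side by side.**

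| Source | Who is in | Adherence condition |
|---|---|---|
| Protocol 8.3.1 | Analysis for the objective | Diary above 60%; weight not below 30% |
| SAP, Methods of Analysis | Analysis for the objective | Diary at least 60%; weight not below 30% |
| Protocol 8.3.3 | Completed at least visit 1 | None |
| Protocol 6.2.3 | Eliminated: non-tolerability, or diary below 50% | Data kept or not: unstated |
| Protocol 8.3.1 and SAP, adverse events | Randomised (Protocol); randomised, after instillation (SAP) | None |

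A subject with 55% diary adherence who attends both visits is not eliminated for adherence. That subject belongs to the 8.3.3 set and fails the filter in both documents. At exactly 60%, the SAP includes the subject and the Protocol does not.

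**3. What happens to a subject who stops for intolerance?** Protocol 8.1.1 allows an attempt at a new or unscheduled visit. Failing that, only adverse events and the reason for stopping are sought, so there is no index. Whether an early stopper passes the filter cannot be settled, because 6.3.2.1 does not say how an unattended interval enters the average.

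**4. Is the case likely to arise?** Protocol 6.6.1 expects at most 10% poor tolerance. If a share *f* of those subjects stop (assumed), the chance of at least one stop among 16 is 1 − (1 − 0.10*f*)^16:

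- *f* = 0.25: 1 − 0.975^16 = 33%
- *f* = 0.50: 1 − 0.95^16 = 56%
- *f* = 1: 1 − 0.90^16 = 81%

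This shows that a rule is likely to be needed. It does not show bias.

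**5. Illustrated size.** The documents give no index SD or effect, so every input except the group size and alpha is assumed. There are 16 subjects per arm and a two-sided Mann-Whitney test at 0.05. Index mean is 40 if intolerant and 15 if not, SD 10, limited to 0–100. The comparator has 5% intolerant, and 80% of intolerant subjects are lost. Results from 10,000 simulated trials:

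| PRO-165 intolerant | Mean difference, all kept / lost | Rejection: all kept | Lost | Worst rank |
|---|---|---|---|---|
| 10% | 1.2 / 0.3 points | 4.8% | 4.5% | 4.8% |
| 25% | 4.9 / 1.3 points | 13.8% | 5.1% | 15.1% |
| 50% | 11.2 / 3.9 points | 53.8% | 9.2% | 59.6% |

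**6. Does keeping these subjects solve it?** The questionnaire (Protocol 14.1) asks about the past week. Someone who stopped in the first days and answers on day 11 or 12 largely describes untreated days. In a separate run at 25% intolerance, with early stoppers' symptoms assumed resolved by then, rejection was 5.3% with them kept, 5.8% with them excluded and 15.5% with the worst rank. The gap between the first two is simulation noise. Redefining the set alone recovers nothing in that case; the worst-rank rule does.

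**The case against.** The strongest reply is that intolerance is not hidden. If recorded as an adverse event it counts in the other primary variable, which has no adherence filter, and success requires no difference on both. That stands, and it confines the defect to one of two primary variables. It does not supply an index score.

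Second, at the protocol's own 10% ceiling the effect on the test is nil for practical purposes. That stands too; rates of 25% to 50% are 2.5 to 5 times what the sponsor expects in healthy volunteers.

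Third, 8.3.1 gives an exposure rationale for the filter, and barely exposed subjects can themselves dilute a difference. This is a reason to keep the adherence-restricted analysis, though not as the only one.

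Fourth, the SAP cites protocol version 2.0 while the protocol is version 4.0, so some mismatches may be version lag. Lag would not explain the conflict between 8.3.1 and 8.3.3 within the protocol. Retention at the investigator's discretion (9.3.1.3) and unscheduled visits reduce the loss without closing the gap.

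A reader might infer three stronger things:

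- **That no analysis set reaches the index.** It is reached through the study objective; the trouble is the conflict with 8.3.3 and the missing rule.
- **That the filter is likely to manufacture a false difference.** That needs very unequal exclusion, such as 80% in one arm and none in the other at equal intolerance. Subject and investigator are blinded and the same criteria apply to both arms. At 80% against 60%, with 25% intolerant in each arm, rejection was 4.8%.
- **That the index result is known to be biased by a given amount.** The documents contain no score data to support any amount.

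**Conclusion.** The concern holds in a limited form, as something that should be fixed. The text establishes, without assumptions, that the index analysis is conditioned on post-randomisation adherence, that this conflicts with the set in 8.3.3, that the two documents differ at exactly 60%, and that no rule covers a missing index or the data of eliminated subjects. Subjects who stop for intolerance can be lost from a comparison in which finding no difference is success.

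The size is unknown. On the assumed scores above, the loss is negligible at 10% intolerance (rejection 4.8% against 4.5%, mean difference 1.2 against 0.3 points) and becomes material only at clearly higher rates, such as 25% (13.8% against 5.1%). Those figures also assume that intolerant subjects would still report high scores at the final visit, which is doubtful for very early stops.

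**What to change.** In Protocol 8.3.1 and 8.3.3 and in the SAP:

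1. Make the primary set for the comfort index all randomised subjects with at least one application, analysed as assigned, regardless of adherence, visit 1 or elimination. Use one definition of intention-to-treat in both documents.
2. Keep the adherence-restricted set as a defined, secondary per-protocol analysis. Reconcile the above-60% and minimum-60% thresholds, and state how they relate to the below-50% elimination criterion.
3. Report discontinuation or elimination for intolerance by arm. Prespecify a Mann-Whitney sensitivity analysis that gives the worst rank to subjects who stopped for intolerance, whether their final index is missing or was taken when the one-week recall no longer covers dosing. Item 1 alone does not recover this information.
4. Optionally, give the questionnaire at discontinuation when the subject attends, noting that after a very early stop much of the recalled week precedes dosing.

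The criteria for stopping treatment stay as they are. The cost is wording, plus, if item 4 is adopted, a six-item questionnaire for the few who stop early and attend, with matching entries in 6.4.4 and 6.5. The downside is slightly more variable index data and possible dilution from barely exposed subjects, which the secondary set will show.

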8.3.2 Additional analyses

No additional analyses beyond those previously described are planned. However, these may be performed if specific safety aspects of an intervention need to be analyzed during the study, maintaining blinding until the study's completion.

8.3.3 Population analysis and missing data handling

An intention-to-treat analysis will be performed, including data from participants who completed at least visit 1.

9. Methods. Monitoring

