6.4 Outcome variables

6.4.1.1 Primary outcome variables

- Security
 - Presence of adverse events.
- Tolerability
 - Eye comfort index

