With a statistical confidence of 95% that corresponds to type I error, equal to 1.96, with a power of 90%, corresponding to type II error, equal to 0.84.

According to the previous calculation, the result is 26 subjects, which was increased by 20% due to the probable losses. The total sample size required is **32 subjects**. So each group will be made up of 16 subjects, who will provide an eye for the analysis.

Analysis Plan [4]

Outcome Variables

Safety primary outcome variables:

- Incidence of Adverse Events.

Primary outcome variables of tolerability:

- ICO score.

Secondary Outcome Variables:

- Tear film rupture time (LRT).
- Vital signs: HR, RF and SAP.
- Posterior segment.
- Quality questionnaire.
- Intraocular pressure.
- Visual capacity.
- Laboratory Tests: BHc, QS, PFH.
- Ocular surface stains.

Table 2. Operational Definition of the Variables

Chondroitin Sulfate 0.18%/Sodium Hyaluronate 0.2%

Variable	Conceptual Definition	Operational Definition	Measurement Type	Normal value	Statistical test
Adverse events (AEs).	Any undesirable medical event that may occur in an investigational subject during the clinical research stage of a drug or vaccine but does not necessarily have a causal relationship with it. ⁴	Adverse events manifested during the conduct of the study will be collected using the CRF.	
 - Continuous quantitative. - Categorical qualitative. 	
 - Frequency: Subjects with AEs/Total number of exposed subjects. - Intensity: 0= Mild 1= Moderate 2= Severe - Causality: 0= Improbably related. 1= Probable or possibly related. 2= Related 	
 - Pearson's square chi or Fisher's exact. - U for Mann-Whitney.
Changes in Intraocular Pressure (IOP).	Tonometry is the objective measurement of IOP, based primarily on the force required to flatten the cornea or the degree of corneal indentation produced by a fixed force.	Goldmann tonometry. 3 samples will be taken, which will be recorded in the clinical file and the average will be recorded in the CRF.	
 - Continuous quantitative. 	
 - 11-21 mmHg. 	
 - U for Mann-Whitney. - Wilcoxon Ranges.

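### The protocol names no analysis set for the deciding adverse-event test, and two general rules (Visit 1 completion, about 60% adherence) can remove subjects who leave early because of an event

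*Protocol*

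**What the plan says.** The primary safety outcome in Protocol 6.4.1.1 is "Presence of adverse events". The rules below bear on who is counted.

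- **Adverse-event reporting, Protocol 8.3.1:** "For adverse event reporting, all eyes of participants randomized to an intervention group after the baseline visit will be considered". There is no Visit 1 condition and no intention-to-treat label.
- **Adverse-event reporting, SAP Methods of Analysis:** all eyes of those "randomly assigned to an intervention group after PI instillation (ITT) will be considered". The adverse-event row of SAP Table 2 gives "Frequency: Subjects with AEs/Total number of exposed subjects" and lists chi-square or Fisher's exact test in the same row.
- **Analysis population, Protocol 8.3.3:** "An intention-to-treat analysis will be performed, including data from participants who completed at least visit 1". This is the only place where the protocol defines an intention-to-treat set. The SAP's abbreviation list expands ITT only as "Population by intent to treat".
- **Adherence, Protocol 8.3.1 and SAP Methods of Analysis:** the analysis that answers the study objective keeps subjects above 60% diary adherence (protocol) or at 60% or more (SAP). In both, a weight-based figure below 30% also excludes.
- **Conclusion rule, both documents:** PRO-165 is safe and tolerable if the primary outcomes show no clinical or statistical difference from the comparator. The sentence names no analysis set.

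The SAP is written against "Protocol Version: 2.0"; the protocol supplied is version 4.0.

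**The concern.** The specific adverse-event sentences and the general population sentences do not agree, and the protocol does not say which governs the test behind the conclusion. If the general rules are applied, a subject who leaves in the first days because of an event is removed from both numerator and denominator. That lowers the event rate in the worse arm and moves the test towards no difference. Since no difference is the favourable result here, the bias runs towards declaring the product safe.

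Such departures are foreseeable. Protocol 6.2.3 lists intolerance or hypersensitivity to the study products, and any serious adverse event, as elimination criteria. The other primary variable, the eye comfort index, is scheduled only at baseline and the final visit (Protocol 6.4.4), so it would not capture someone who left before then. Among the primary outcomes, early intolerance can therefore show only in the adverse-event comparison.

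**Working it through.** **1. Who each rule keeps.**

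| Rule | Dosed, leaves before Visit 1 | Attends Visit 1, stops by day 5 | Randomised, never dosed |
|---|---|---|---|
| Protocol 8.3.1, event reporting | kept | kept | kept |
| SAP, event reporting | kept | kept | not kept |
| Protocol 8.3.3, Visit 1 completers | dropped | kept | dropped if Visit 1 is missed |
| Adherence filter, both documents | dropped | dropped (step 2) | dropped |

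The two reporting rules differ only on never-dosed subjects. The early leavers are lost through the last two rows.

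**2. Adherence of an early stopper.** Inputs: 4 applications a day for 10 days (Protocol 1 and 6.3.1), so 4 × 10 = 40. Adherence = recorded applications × 100 / indicated applications (Protocol 6.3.2.1).

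- Stop after day 2: 8/40 = 20%.
- Stop after day 5: 20/40 = 50%, below both thresholds.
- Stop after day 6: 24/40 = 60%, which fails the protocol (more than 60%) and meets the SAP (at least 60%).

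This takes all 40 applications as the denominator. Protocol 6.3.2.1 also says that final adherence is the average over visits. If the period after Visit 1 is scored on its remaining applications, a subject who stops after day 5 with Visit 1 on day 3 gets (12/12 + 8/28)/2 = 64% and passes. With Visit 1 on day 4 the figure is (16/16 + 4/24)/2 = 58%, and a later Visit 1 gives less. Stopping after day 4 gives at most (12/12 + 4/28)/2 = 57%. So on either method a subject who stops by day 4 fails both thresholds. If a period without a returned diary were left out of the average, the filter would catch fewer; the plan does not say.

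**3. Effect on the test.** The plan gives no event counts by arm, so it has no figure of its own to reproduce here. I use 16 per group (Protocol 6.6.1), alpha 0.05, two-sided Fisher's exact test (sidedness is not stated) and assumed counts.

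- All dosed, 5/16 v 0/16: C(16,5)/C(32,5) = 4368/201376 = 0.0217 in each tail, so p = 0.043.
- One event case dropped, 4/15 v 0/16: C(15,4)/C(31,4) = 1365/31465, so p = 0.043. The opposite tail is more probable and is not added.
- Two dropped, 3/14 v 0/16: C(14,3)/C(30,3) = 364/4060, so p = 0.090.
- A second example: 7/16 v 1/16, p = 0.037; 6/15 v 1/16, p = 0.037; 5/14 v 1/16, p = 0.073.

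The observed rate in the first example goes from 31% (5/16) to 27% (4/15) to 21% (3/14).

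**4. Chance of a significant result.** Exact calculation; each subject with an event leaves the analysed set with the stated probability, the same in both arms.

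| Assumed true rates | None leave | 25% leave | 50% leave |
|---|---|---|---|
| 50% v 5% | 78% | 71% | 49% |
| 25% v 10% | 9.7% | 8.8% | 4.4% |

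The second row uses the two percentages in Protocol 6.6.1; the first is a large difference chosen for illustration. At a true rate of 50%, the rate among those kept falls to 0.375/0.875 = 43% with 25% leaving and 0.25/0.75 = 33% with 50% leaving.

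**The case against.** The strongest answer is that a specific rule governs over a general one. Protocol 8.3.3 does not mention adverse events, the event sentences in both documents carry no visit condition, and SAP Table 2 puts the between-arm test beside an exposed-subjects denominator. On that reading nobody is lost and the documents differ only on instillation: one never-dosed subject moves 5/16 (31.3%) to 5/15 (33.3%), about 2 points. This is a fair reading, and probably the intended one. It does not settle the matter. The protocol's event sentence speaks of reporting, its conclusion rule names no set, and the adherence sentences in both documents claim the analysis that meets the objective without exempting adverse events.

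Three stronger readings are tempting, and the documents do not support them.

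- That the protocol defines its adverse-event set as Visit 1 completers. It does not; loss of early leavers is a risk from conflicting rules, not a stated instruction.
- That the SAP's ITT label brings in Protocol 8.3.3. The SAP describes its set where it uses the label, does not refer to 8.3.3, and cites another protocol version.
- That anyone who stops on days 1 to 6 is absent from the 8.3.3 set. That set depends on completing a visit due on days 3 to 7, not on staying on treatment, and a subject who has stopped may still attend.

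Protocol 8.1.1 also requires the site to ask about adverse events when a missed appointment cannot be rescheduled. That secures the data but does not place the subject in the analysed set.

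It is also fair to say that the Fisher examples need two lost event cases in one arm, and that at 25% v 10% the test rarely finds a difference in any set.

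**Conclusion.** The conflict stands as an ambiguity that should be removed. ITT means Visit 1 completers in the protocol and instilled subjects in the SAP, and a set that depends on attending a visit after dosing is not intention-to-treat. The protocol names no set for the deciding test. The adherence filter is the wider route for losing early stoppers, because it also removes some who attended Visit 1, so aligning the ITT label alone would not solve the problem.

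The direction of the bias is clear: towards no difference, and so towards safe. Its size is conditional. In the examples, two dropped event cases change the result and one does not. With a large true difference (50% v 5%) the chance of detecting it falls by 7 to 29 points; at 25% v 10% it is below 10% throughout, so the choice of set would seldom change the conclusion. Event counts, rates and shares leaving are assumptions. The adherence step assumes that unused applications count against the subject.

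**What to change.** Define one safety set, in the same words in both documents: every randomised subject with at least one application, analysed as randomised, with no Visit 1 condition and no adherence condition. State that it serves both the adverse-event tables and the between-arm adverse-event test in the conclusion rule. List never-dosed subjects separately.

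In Protocol 8.3.3, keep the Visit 1 condition for other analyses only and stop calling that set intention-to-treat. In Protocol 8.3.1 and the SAP's Methods of Analysis, state that the adherence thresholds do not apply to the adverse-event analysis, and reconcile more than 60% with at least 60%. Update the protocol version that the SAP cites.

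The cost is a few sentences. No new data are needed, because the safety call and the missed-visit call already ask about adverse events. The reported event rate may be less favourable. The change does not cure the low power of the comparison.
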